- To determine the 4 β -hydroxycholesterol to cholesterol concentration ratios as a marker of CYP3A4 induction by rifampicin.
- To further assess the safety and tolerability of selumetinib by the assessment of adverse events, laboratory variables, and vital signs.

Exploratory Objective

To collect an optional pharmacogenetic blood sample from consenting volunteers for exploratory investigation to determine the variability in PK or safety parameters can be explained by differences in the healthy volunteer's genotype.

The exploratory analysis will be reported separately.

Study design

This clinical study is designed as a Phase I, open-label, fixed sequence, single-center study to investigate the effect of rifampicin (a known CYP3A4 inducer) on the PK, safety and tolerability of a single 75 mg oral dose of selumetinib in healthy volunteers. Approximately 24 healthy male and female (of non-childbearing potential) volunteers aged between 18 to 45 years (inclusive), will be enrolled in the study. Withdrawn healthy volunteers will not be replaced; however, additional volunteers may be included in the study until such a time as 20 evaluable volunteers have completed both treatments. Screening procedures will only be performed for healthy volunteers who provide written informed consent.

The study will consist of 3 visits. Visit 1 will be a screening visit and will take place within 28 days of Visit 2. Visit 2 will be the treatment visit and the healthy volunteers will be resident at the study center from Day -1 up to Day 15. Visit 3 will be the follow-up visit and will take place 7 to 10 days after discharge on Day 15, Visit 2.

Healthy volunteers will be assigned to the following treatment schedule:

- Treatment A: Healthy volunteers will receive a single oral dose of 75 mg (3 x 25 mg) selumetinib on Day 1. Safety assessments will be performed and blood samples collected for PK analysis until Day 4.
- Treatment B: Following completion of assessments for Treatment A on Day 4, volunteers will receive single, daily, oral doses of 600 mg (2 x 300 mg) rifampicin on Days 4 to 11.
- Treatment C: On Day 12, volunteers will receive 600 mg (2 x 300 mg) rifampicin with a single oral dose of 75 mg (3 x 25 mg) selumetinib administered at the same time. Once daily rifampicin administrations will continue through to Day 14.

Safety assessments will be performed and blood samples collected for PK analysis until Day 15.

Target subject population

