Healthy male and female (of non-childbearing potential) volunteers aged 18 to 45 years (inclusive) who are non-smokers, have a body mass index (BMI) between 18 and 30 kg/m² (inclusive) and weigh at least 50 kg and no more than 100 kg (inclusive), have a calculated creatinine clearance greater than 50 mL/min using the Cockcroft-Gault formula. Healthy volunteers with current or past history of central serous retinopathy or retinal vein thrombosis, intra-ocular pressure greater than 21 mmHg or uncontrolled glaucoma will be excluded.

Investigational product, dosage and mode of administration

A single administration of 75 mg selumetinib will be administered as 3 x 25 mg oral capsules (Treatment A).

Comparator, dosage and mode of administration

Healthy volunteers will receive single daily oral doses of 600 mg (2 x 300 mg) rifampicin on Days 4 to 11 and Days 13 to 14 (Treatment B). On Day 12, the volunteers will receive 600 mg (2 x 300 mg) rifampicin and 75 mg (3 x 25 mg) selumetinib at the same time (Treatment C).

Duration of treatment

Volunteers will participate in the study for approximately 8 weeks; including screening over 28 days. Volunteers will be resident in the study center from Day -1 until all study assessments are completed on Day 15, with a follow-up visit 7 to 10 days after discharge (Day 15).

Outcome variable(s):

- Pharmacokinetics

The primary PK parameters will be: maximum observed plasma concentration (C_{max}), area under the plasma concentration-time curve from time zero to infinity (AUC), and area under plasma concentration-time curve to time of last measurable concentration ($AUC_{(0-t)}$).

The secondary PK parameters will be: time to reach maximum observed concentration administration (t_{max}), area under the plasma concentration time curve from zero to 12 hours post-dose ($AUC_{(0-12)}$), terminal rate constant (λ_z), terminal elimination half-life ($t_{1/2}$), apparent oral clearance (CL/F), apparent volume of distribution at steady state (V_{ss}/F), apparent volume of distribution during the terminal phase (V_z/F), and mean residence time (MRT) for selumetinib, and AUC, C_{max} , t_{max} , $t_{1/2}$, λ_z , AUC_{0-12} , $AUC_{(0-t)}$, and the metabolite to parent AUC and C_{max} ratios (MR_{AUC} and $MR_{C_{max}}$) for N-desmethyl selumetinib.

Pharmacokinetic parameters will not be determined for rifampicin. Only the 2 hours post-dose plasma concentrations will be reported.

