3.1 Overall study design and flow chart

This clinical study is designed as a Phase I, open-label, fixed sequence, single-center study to investigate the effect of rifampicin (a known CYP3A4 inducer) on the PK, safety and tolerability of a single 75 mg oral dose of selumetinib in healthy male and female (of non-childbearing potential) volunteers. Approximately 24 healthy volunteers aged between 18 to 45 years (inclusive), will be enrolled in the study. Withdrawn healthy volunteers will not be replaced; however, additional volunteers may be included in the study until such a time as 20 evaluable volunteers have completed both treatments. Screening procedures will only be performed for healthy volunteers who provide written informed consent.

The study will consist of 3 visits. Visit 1 will be a screening visit and will take place within 28 days of Visit 2. Visit 2 will be the treatment visit and the healthy volunteers will be resident at the study center from Day -1 up to Day 15. Visit 3 will be the follow-up visit and will take place 7 to 10 days after discharge on Day 15, Visit 2.

Healthy volunteers will be assigned to the following treatment schedule:

- Treatment A: Healthy volunteers will receive a single oral dose of 75 mg (3 x 25 mg) selumetinib on Day 1. Safety assessments will be performed and blood samples collected for PK analysis until Day 4.
- Treatment B: Following completion of assessments for Treatment A on Day 4, volunteers will receive single, daily, oral doses of 600 mg (2 x 300 mg) rifampicin on Days 4 to 11.
- Treatment C: On Day 12, volunteers will receive 600 mg (2 x 300 mg) rifampicin with a single oral dose of 75 mg (3 x 25 mg) selumetinib administered at the same time. Once daily rifampicin administration will continue through Day 14.

Safety assessments will be performed and blood samples collected for PK analysis until Day 15.

The study flow chart is presented in [Figure 1](#)

Figure 1 Study flow chart

[figure not shown]

Table 2 Study plan

Days	Visit 1				Visit 2					Visit 3	
	Screening	Treatment A (selumetinib only)			Treatment B (rifampicin only)			Treatment C (selumetinib +rifampicin)		Discharge	Follow-up visit
	-28 to -2	-1	1	2 to 3	4	5 to 10	11	12	13 to 14	15	7 to 10 days after discharge
Informed consent	X										
Optional informed consent for genotyping ^j		X ^j									
Demographic data	X										
Medical/surgical history	X										
Hepatitis B, C, and HIV screen	X										

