5.5.2 Doses and treatment regimens

The dose level of 75 mg of selumetinib (3 x 25 mg capsules) is considered to be in the therapeutic dose range and is the maximum dose permitted in healthy volunteers. A dose of 75 mg twice daily is being investigated in ongoing efficacy studies of selumetinib.

Daily administrations of 600 mg (2 x 300 mg) rifampicin oral capsules for 9 days will maximize the induction effect on CYP3A4.

Treatment A (selumetinib alone):

A single administration of 75 mg selumetinib will be administered as 3 x 25 mg oral capsules in the fasted state. Healthy volunteers will be fasted overnight for at least 10 hours before receiving selumetinib and until 4 hours post-dose. No fluids will be allowed from 1 hour before investigational product administration until 1 hour after investigational product administration, except for water needed to swallow the investigational product. Standardized meals (lunch, dinner, and a snack) will be provided at the same time during Visit 2.

Treatment B (rifampicin):

Healthy volunteers will receive single daily oral doses of 600 mg (2 x 300 mg) rifampicin as capsules on Days 4 to 11 under food restriction where they will be fasted overnight for at least 10 hours before receiving rifampicin and until 1 hour post-dose. Standardized meals (lunch, dinner, and a snack) will be provided at the same time during Visit 2. No fluids will be allowed from 1 hour before investigational product administration until 1 hour after investigational product administration, except for water needed to swallow the investigational product.

Treatment C (rifampicin + selumetinib):

On Day 12, healthy volunteers will receive 600 mg (2 x 300 mg) rifampicin oral capsules and 75 mg (3 x 25 mg) selumetinib oral capsules in the fasted state (fasted from midnight on Day 11 to 4 hours after investigational product administration) administered at the same time. Healthy volunteers will continue to receive single daily oral 600 mg (2 x 300 mg) doses of rifampicin on Days 13 to 14 under food restriction where they will be fasted overnight for at least 10 hours before receiving rifampicin and until 1 hour post-dose. Standardized meals (lunch, dinner, and a snack) will be provided at the same time during Visit 2. No fluids will be allowed from 1 hour before investigational product administration until 1 hour after investigational product administration, except for water needed to swallow the investigational product.

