6.4.1.1 Selumetinib and metabolite

Blood samples (2 mL total at each timepoint) to measure selumetinib and N-desmethyl metabolite collected predose, and 0.5, 1, 1.5, 2, 2.5, 3, 4, 5, 6, 8, 12, 24, 36, 48 & 72 hours after the selumetinib administration on Days 1 and 12. If deemed appropriate, the amide metabolite may also be measured. The number of blood samples collected is 16 per study period, for a total of 32.

The selumetinib PK blood sample collected 72 hours post-dose on Day 4 will be collected prior to the administration of rifampicin.

Rifampicin and selumetinib are administered at the same time on Day 12. The blood samples collected for selumetinib PK at the 24 and 48 hours post-dose timepoints will likely coincide with rifampicin administrations on Day 13 and Day 14. While selumetinib blood sample collections should be captured on time, relative to the time of selumetinib dose administration, should these collections and the time for rifampicin dose administration coincide, the selumetinib PK blood sample should be collected prior to the dose of rifampicin.

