12. STATISTICAL METHODS AND SAMPLE SIZE DETERMINATION

12.1 Description of analysis sets

12.1.1 Safety analysis set

All healthy volunteers who received at least 1 administration of investigational product (selumetinib or rifampicin) will be included in the safety population.

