12.2.2 Safety and tolerability

All safety data (scheduled and unscheduled) will be presented in the data listings. Continuous variables will be summarized using descriptive statistics (n, mean, SD, minimum, median, maximum) by treatment. Categorical variables will be summarized in frequency tables (frequency and proportion) by treatment.

Safety variables (eg, clinical laboratory values and vital signs) will be reported to the same precision as the source data. Derived variables will be reported using similar precision to those from which they were derived.

Extra measurements (such as unscheduled or repeat assessments) will not be included in the descriptive statistics by scheduled time point, but will be included in data listings. All AEs and clinical laboratory outliers that occur following the first dose of investigational product will be included in the analyses of AEs and outlier events, including episodes that occur at unscheduled evaluations, evaluations, or during the washout period.

All available data from healthy volunteers in the safety analysis set will be included in the safety analyses.

All AEs will be collected for each healthy volunteer from Day -1 Visit 2 until the follow-up visit. All SAEs will be collected for each healthy volunteer from the time when informed consent is obtained until the follow-up visit.

Adverse events will be listed for all healthy volunteers with AEs that occur before investigational product administration indicated on the listing. The number of AEs experienced following administration of the investigational product will be summarized in tables using the Medical Dictionary for Regulatory Activities (MedDRA) (Version 13.0 or higher) System Organ Class and Preferred Term. These summary tables will also be produced with severity and causality of AEs added as additional classification factors. The number of AEs overall, SAEs, OAEs, AEs that lead to withdrawal, AEs of severe intensity, and causally-related AEs will be summarized. Any AE occurring post-dose will be considered associated with the last administration of investigational product taken. Any AE occurring on Visit 2 Day -1 will not be included in the summaries.

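### The rule tying each AE to the last product taken, with Days 13-14 labelled both Treatment B and Treatment C, leaves the combination's AE window undefined: about 24 hours or 10-13 days, against 72 hours for selumetinib alone

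*Protocol*

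**What the plan says.** Section 12.2.2 gives the attribution rule: "Any AE occurring post-dose will be considered associated with the last administration of investigational product taken". Its unit is an administration, not a treatment period.

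Section 12.1.1 defines the safety set by receipt of "at least 1 administration of investigational product (selumetinib or rifampicin"), so rifampicin is investigational product for safety purposes. The drug table in Section 5.5.3 also lists rifampicin under that column heading.

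Rifampicin continues by itself after the Day 12 combined dose, and four places put those doses in Treatment C:

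- Section 3.1, Treatment C bullet: "Once daily rifampicin administration will continue through Day 14".
- Synopsis, study design, Treatment C bullet: "Once daily rifampicin administrations will continue through to Day 14".
- Section 5.5.2, under the Treatment C heading: "Healthy volunteers will continue to receive single daily oral 600 mg (2 x 300 mg) doses of rifampicin on Days 13 to 14".
- Table 2, whose column header, as far as the layout can be read, groups Days 13 to 14 with Day 12 under Treatment C.

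The comparator paragraph of the synopsis says otherwise. It describes "rifampicin on Days 4 to 11 and Days 13 to 14 (Treatment B") and keeps the Treatment C label for Day 12 only.

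On timing, Section 6.4.1.1 notes that the "24 and 48 hours post-dose timepoints will likely coincide with rifampicin administrations on Day 13 and Day 14". The synopsis and Section 12.2.2 plan AE and other safety summaries by treatment, and AE collection runs to the follow-up visit.

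**The concern.** From the Day 13 dose onwards, the last product a volunteer has taken is rifampicin alone. If that decides the table column, an event 30 to 72 hours after the combined dose, or one found at follow-up, is counted under rifampicin alone even though selumetinib was given within the preceding three days or so. If the column is instead decided by the treatment that contains the Day 13-14 doses, the answer depends on which label for those doses is used, and the protocol gives two.

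Further assessment of selumetinib safety and tolerability is a stated secondary objective, and AE summaries by treatment are a main output for it. Two programmers following the same protocol could produce materially different AE tables from the same data. Under neither reading would selumetinib alone and selumetinib with rifampicin be compared over the same length of time.

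**Working it through.** The protocol states no figure for AE windows, so there is none to reproduce. The check sets the rule against the dosing calendar.

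**Inputs**

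- Selumetinib alone: Day 1 (Section 3.1).
- First rifampicin dose: Day 4, after the 72-hour sample (Section 6.4.1.1).
- Combination: Day 12. Rifampicin alone on Days 13 and 14, about 24 and 48 hours later (Sections 5.5.2 and 6.4.1.1).
- Discharge: Day 15. Follow-up 7 to 10 days later (Section 3.1).

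**Window for Treatment A, the same on every reading**

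Day 4 − Day 1 = 3 days = 72 hours.

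**End of AE collection**

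Day 15 + 7 = Day 22; Day 15 + 10 = Day 25. Measured from the Day 12 dose: 22 − 12 = 10 days; 25 − 12 = 13 days.

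**Reading 1: by single dose, or with Days 13-14 labelled Treatment B**

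- Combination: Day 13 − Day 12 = 1 day, about 24 hours.
- Relative to Treatment A: 24/72 = one third.
- Share of the period from the combined dose to follow-up: 1/13 = 7.7% to 1/10 = 10%.
- Credited to rifampicin alone after the combination: 22 − 13 = 9 days to 25 − 13 = 12 days, in addition to Day 4 up to the Day 12 dose.

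**Reading 2: Days 13-14 inside Treatment C**

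- Combination: 10 to 13 days, or 240 to 312 hours.
- Relative to Treatment A: 240/72 = 3.3 to 312/72 = 4.3 times as long.
- Moved to rifampicin alone after the combination: nothing.

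**Side by side**

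| | Reading 1 | Reading 2 |
|---|---|---|
| Selumetinib alone (A) | 72 h | 72 h |
| Selumetinib + rifampicin (C) | about 24 h | 10-13 days |
| C relative to A | one third | 3.3 to 4.3 times |
| Rifampicin alone after Day 12 | 9-12 days | none |

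The combination's time at risk differs 10- to 13-fold between the readings, and the imbalance against Treatment A changes direction. Under Reading 1, Treatment C has less time than A to collect events; under Reading 2 it has more.

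**Is a common window available?** The first 72 hours after selumetinib run from Day 1 to Day 4 in Treatment A and from Day 12 to Day 15 in Treatment C (12 + 3 = 15). Volunteers are resident throughout both, so a like-for-like table can be built from data already planned.

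**The case against.** The strongest reply is that the rule only links an AE to a dose, while the tables count by treatment. Since the synopsis design text, Section 3.1, Section 5.5.2 and Table 2 all put the Day 13-14 doses in Treatment C, a late AE links to a Treatment C dose and is tabulated there. On that view the synopsis comparator paragraph is one stray label and nothing is misallocated. This largely stands. A reader might infer from Section 12.2.2 that AEs later than about 24 hours after the combination are simply credited to rifampicin, and that the comparison is biased against finding events on the combination. The documents do not support that as an unconditional statement. It needs either a dose-by-dose reading or the Treatment B label, and no AE tables by individual product are planned.

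The reply does not make the rule sound, however. Section 12.2.2 does not say whether the last administration means the dose or the treatment it belongs to, the contradictory label remains, and the favoured reading still compares 10 to 13 days with 72 hours.

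Two further replies limit the impact. AE start and stop times are recorded and all AEs are listed, so events can be re-tabulated and no data are lost; that is correct. The investigator's causality rating is also recorded separately. But Section 6.3.3 describes it as one yes/no answer against the investigational product, a term that covers both drugs in Section 12.1.1, so as described it does not separate selumetinib from rifampicin.

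Exact AE windows are often left to an analysis plan, and the absence of a common-window table is not in itself an error. Here, though, the protocol itself fixes the attribution rule and itself contradicts the label, so an analysis plan that follows it inherits both.

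**Conclusion.** The point holds as an ambiguity with a material effect on the AE tables. Depending on the reading, the AE window for selumetinib with rifampicin is about 24 hours or 10 to 13 days, against 72 hours for selumetinib alone. It is unequal both ways, and the direction of the imbalance is not determined by the protocol. The one-third and 8-10% figures describe one reading only and should not be quoted as the expected result; the larger part of the text favours the other.

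The sizes assume that rifampicin is given at about the same clock time each day, that follow-up falls within its 7 to 10 day range, and that windows are counted in whole days from dosing.

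This should be fixed, but it is not critical. Safety is a secondary objective summarised descriptively, Section 12.2.3.1 disclaims powering for formal hypothesis testing, and the primary PK analysis is unaffected.

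**What to change.** Three changes, made before the AE tables are programmed:

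1. Reconcile the label for the Day 13-14 rifampicin doses in the synopsis comparator paragraph with the synopsis design text, Section 3.1, Section 5.5.2 and Table 2. This concerns the treatment label used in analysis, not the dosing.
2. In Section 12.2.2, attribute AEs by treatment period instead of by last single administration: Treatment A from the Day 1 dose to just before the Day 4 rifampicin dose; Treatment B from then to just before the Day 12 dose; Treatment C from the Day 12 dose to follow-up. State explicitly that AEs from Day 13 to follow-up are counted under Treatment C.
3. Because those periods differ in length, add a table of Treatment A and Treatment C AEs over the common 0-72 hours after each selumetinib dose.

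The cost is a wording change and one extra descriptive table. Dosing, visits and data collection do not change.

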12.2.3 Pharmacokinetics

A listing of PK blood sample collection times as well as derived sampling time deviations will be provided for each analyte, as appropriate.

12.2.3.1 Selumetinib and metabolites

Pharmacokinetic variables will be summarized using appropriate descriptive statistics (eg, number, arithmetic mean, CV%, SD, geometric mean, geometric coefficient of variation [GCV%], minimum, median, and maximum). The geometric mean is calculated as the exponential of the arithmetic mean calculated from individual observations on a log scale.

The GCV% is calculated as $100 \cdot \sqrt{(\exp(s^2) - 1)}$ where s is the SD of the data on a log scale. Mean, SD, CV%, geometric mean, and GCV% will not be calculated for t_{max} .

Plasma concentrations that are below the lower limit of quantification (LLOQ) will be handled as follows:

- At a time point where less than or equal to 50% of the values are below the LLOQ (BLQ), all BLQ values will be set to LLOQ, and all descriptive statistics will be calculated.
- At a time point where more than half of the values are BLQ, the mean, SD, geometric mean, and CV% will be set to Not Determined (ND). The maximum value will be reported from the individual data, and the minimum and median will be set to BLQ.
- If all values are BLQ at a time point, no descriptive statistics will be calculated for that time point. Not applicable will be written in the field for SD and CV% and BLQ will be written in fields for mean, geometric mean, minimum, median, and maximum.
- The number of BLQ values (n below LLOQ) will be reported for each time point.

A subject listing of all concentration-time data will be presented along with the descriptive statistics for all healthy volunteers. Data from healthy volunteers excluded from an analysis set will be included in the data listings, but not in the summaries. A listing of PK blood sample collection times as well as derived sampling time deviations will be provided. Figures of geometric mean (\pm geometric SD) concentration-time data will be graphically presented on linear and semi-logarithmic scales.

Pharmacokinetic parameters will be summarized and presented graphically, as appropriate, using descriptive statistics by treatment and analyte. Scatter plots of the individual parameter data (C_{\max} , AUC, and $AUC_{(0-t)}$) and geometric means will be presented by analyte, treatment, and parameter, with lines connecting the individual parameters and geometric means across the two treatments under comparison. Graphical presentations of other PK data may be added at the discretion the pharmacokineticist.

Following log-transformation of selumetinib C_{\max} , AUC and AUC_{0-t} will be separately analyzed by mixed effect analysis of variance, fitting a fixed effect term for treatment (selumetinib + rifampicin vs selumetinib alone) and random effects for volunteer. Point estimates and adjusted 90% confidence interval (CI) for the difference in treatment (selumetinib + rifampicin or selumetinib alone) will be constructed. The point estimate and adjusted 90% CIs will then be exponentially back transformed to provide point and CI estimates for the ratio of interest (ie, C_{\max} or AUC of selumetinib contrasting with or without co-administration with rifampicin).

Analyses will be conducted for selumetinib and separately for the metabolite N-desmethyl selumetinib. However, note that sample size was determined according to the precision of the drug-drug interactions effect on selumetinib, rather than the metabolite.

Although descriptive CIs will be presented for some outcomes, this study has not been powered to perform any formal hypothesis testing.

